9.1.4. Simulation Codes (in R)

```

#type-I error simulation program:
nsim=1000000
mu=1
sd=3
nIA=ceiling(368*2/3*0.73)
alpha=0.049
t=2/3 #information fraction of the IA;
Nmax=528
r=Nmax/368
Cb=qnorm(1-alpha/2)+qnorm(0.9)

res=sapply(1:nsim, function(x) {
  set.seed(x)
  #simulate 368*2/3*0.73 IA subjects from the null hypothesis
  y=rnorm(nIA, mean=mu, sd=sd)
  y_p=y[1:(nIA/2)]
  y_t=y[-(1:(nIA/2))]

  #d is planned difference;
  d=1
  var_pool=mean(c(var(y_t), var(y_p)))

  delta_fac=Cb
  N.new=ceiling(4*var_pool*delta_fac^2/d^2/0.73)
  N.new=ceiling(N.new/2)*2

  N.new=ifelse(N.new>Nmax, Nmax, ifelse(N.new<368, 368, N.new))
  #then simulate more samples based on the new sample size
  N.new_nonmiss=ceiling(N.new*0.73/2)*2
  Ndelta=N.new_nonmiss-nIA
  y_p_final=c(y_p, rnorm(Ndelta/2, mean=mu, sd=sd))
  y_t_final=c(y_t, rnorm(Ndelta/2, mean=mu, sd=sd))

  test.sim=t.test(y_p_final, y_t_final)

  return(c(N.new, test.sim$p.value))
})
res=t(res)
alpha_sim=mean(res[,2]<alpha)
mean(res[,1]==368)
mean(res[,1]==528)

```

```

mean(res[,1])
range(res[,1])

#power simulation program:
nsim=1000000
mu_p=0
mu_t=1
d_p=1  #planned difference for sample size estimation

sd=2.5
nIA=ceiling(368*2/3*0.73)
alpha=0.049
t=2/3 #information fraction of the IA;
Nmax=528
r=Nmax/368
Cb=qnorm(1-alpha/2)+qnorm(0.9)

#power simulations:
res=apply(1:nsim, function(x) {
  set.seed(x)
  #simulate 368*2/3*0.73 IA subjects from the null hypothesis
  y_p=rnorm(nIA/2, mean=mu_p, sd=sd)
  y_t=rnorm(nIA/2, mean=mu_t, sd=sd)

  var_pool=(var(y_t)+var(y_p))/2
  delta_fac=Cb
  N.new=ceiling(4*var_pool*delta_fac^2/d_p^2/0.73)
  N.new=ceiling(N.new/2)*2
  N.new=ifelse(N.new>Nmax, Nmax, ifelse(N.new<368, 368, N.new))
  #then simulate more samples based on the new sample size
  N.new_actual=ceiling(N.new*0.73/2)*2
  Ndelta=N.new_actual-nIA
  y_p_final=c(y_p, rnorm(Ndelta/2, mean=mu_p, sd=sd))
  y_t_final=c(y_t, rnorm(Ndelta/2, mean=mu_t, sd=sd))
  d_final=mean(y_t_final)-mean(y_p_final)

  test.sim=t.test(y_p_final, y_t_final)
  return(c(N.new, d_final, test.sim$p.value))
})
res=t(res)
alpha_sim=mean(res[,3]<alpha)
bias=mean(res[,2])-1

mean(res[,1]==368)
mean(res[,1]==528)
mean(res[,1])
range(res[,1])

```

9.2. Schedule of Assessments

Table 7: Schedule of Assessments

Trial Period:	Screen	Baseline	Treatment									Safety Follow-up ^a
Trial Week:	-4 to -1	1	2	5	8	11	14	18	22	26	27 ^b	31
Trial Day:	-31 to -1	1	14±3	35±3	56±3	77±3	98±3	126±3	154±3	182±3	189±3	217±3
Visit/Contact:	Visit 1	Visit 2	Visit 3	Visit 4	Visit 5	Visit 6	Visit 7	Visit 8	Visit 9	Visit 10	Visit 11 (EOT/ET)	Telephone ^c
Entrance and History												
Informed consent ^d	X											
Eligibility criteria	X	X										
Demography	X											
Psychiatric history ^e	←-----→											
Medical history ^e	←-----→											
Alcohol/illicit drug use inquiry	X											
Modified Hoehn and Yahr stage	X						X			X	X	
MoCA	X											
Randomization		X										
Efficacy and Other Endpoint Assessments												
Hauser diary training video and on/off time concordance testing ^f	X											
Dispense Hauser diary ^g	X	X	X	X	X	X	X	X	X	X	X	
Collect/review Hauser diary ^g		X	X	X	X	X	X	X	X	X	X	
MDS-UPDRS ^h	X	X		X	X	X	X	X	X	X	X	
PDQ-39		X								X	X	
EQ-5D-5L		X					X			X	X	
Safety Assessments												
ESS		X	X	X	X	X	X	X	X	X	X	

Trial Period:	Screen	Baseline	Treatment										Safety Follow-up ^a
			2	5	8	11	14	18	22	26	27 ^b	31	
Trial Week:	-4 to -1	1											
Trial Day:	-31 to -1	1	14±3	35±3	56±3	77±3	98±3	126±3	154±3	182±3	189±3	217±3	
Visit/Contact:	Visit 1	Visit 2	Visit 3	Visit 4	Visit 5	Visit 6	Visit 7	Visit 8	Visit 9	Visit 10	Visit 11 (EOT/ET)	Telephone ^c	
QUIP-RS		X	X	X	X	X	X	X	X	X	X		
C-SSRS ⁱ	X	X	X	X	X	X	X	X	X	X	X		
Physical/neurological examination ^j	X											X	
Weight	X	X										X	
Vital signs ^k	X	X	X	X	X	X	X	X	X	X	X		
Single 12-lead ECG ^l	X	X		X		X	X		X			X	
One set of triplicate ECGs prior to first dose of IMP ^m		X											
Eye examination						X ^w						X ^x	
Prior/concomitant medications		←-----→											
Adverse events ⁿ		←-----→											
Laboratory^o													
Safety laboratory blood sample	X	X				X			X		X		
Prolactin level		X ^v										X ^v	
Serology (HIV, HbsAg, and HCV)	X												
Dipstick urinalysis ^p	X	X			X			X			X		
Serum pregnancy test ^q	X												
Urine dipstick pregnancy test ^q		←-----→											
Urine drug screen ^r	X	←-----→										X	
Plasma PK sample ^s		X		X		X	X		X			X	
Future biospecimen research blood sample ^t		X											

Trial Period:	Screen	Baseline	Treatment									Safety Follow-up ^a
			1	2	5	8	11	14	18	22	26	
Trial Week:	-4 to -1	1	2	5	8	11	14	18	22	26	27 ^b	31
Trial Day:	-31 to -1	1	14±3	35±3	56±3	77±3	98±3	126±3	154±3	182±3	189±3	217±3
Visit/Contact:	Visit 1	Visit 2	Visit 3	Visit 4	Visit 5	Visit 6	Visit 7	Visit 8	Visit 9	Visit 10	Visit 11 (EOT/ET)	Telephone ^c
IMP Administration and Compliance ^u												
Dispense IMP		X	X	X	X	X	X	X	X	X		
Assess IMP compliance			X	X	X	X	X	X	X	X	X	

Abbreviations: C-SSRS = Columbia-Suicide Severity Rating Scale, ECG = electrocardiogram, eCRF = electronic case report form, EQ-5D-5L = EuroQol 5 Dimension 5 Level, ESS = Epworth Sleepiness Scale, EOT = end of treatment, ET = early termination, HbsAg = hepatitis B surface antigen, HCV = hepatitis C virus, HIV = human immunodeficiency virus, IMP = investigational medicinal product, L-Dopa = levodopa, MDS-UPDRS = Movement Disorder Society – Unified Parkinson’s Disease Rating Scale, MoCA = Montreal Cognitive Assessment, PDQ-39 = 39-Item Parkinson’s Disease Questionnaire, PK = pharmacokinetic, QUIP-RS = Questionnaire for Impulsive-Compulsive Disorders in Parkinson’s Disease-Rating Scale.

- a. Subjects who prematurely discontinue from the trial or who are not eligible for or choose not to participate in the open-label extension trial (Protocol CVL-751-PD-004) are to participate in the 4-week Safety Follow-Up Period. Subjects who proceed into the open-label extension trial will go directly into that trial and will not complete the Safety Follow-up Period.
- b. The assessments scheduled for the Week 27 visit are to be performed for any subject who prematurely discontinues from the trial.
- c. Contact with subjects via telephone call or other means of communication to check on their status.
- d. Informed consent must be obtained before any trial-related procedures are performed.
- e. Medical occurrences that begin before the start of IMP dosing but after obtaining informed consent will be recorded as medical and/or psychiatric history.
- f. Subjects and investigators (or qualified designees) will independently complete concordance testing. Full details and requirements for the conduct and successful completion of concordance testing are provided in the appropriate protocol-specific manual.
- g. Subjects will record entries for 24 hours on 2 consecutive days within the 7 days before randomization at the Baseline Visit, after diary training and concordance testing has occurred. Subject will record entries for 24 hours on 2 consecutive days within the 7 days before each postbaseline clinic visit.
- h. MDS-UPDRS Parts I, II, and III should be conducted approximately 2 to 3 hours after the last dose of L-Dopa on that day.
- i. The “Baseline/Screening” C-SSRS form will be completed at the Screening Visit to determine eligibility. The “Since Last Visit” C-SSRS form will be completed at the Baseline Visit to ensure that the subject continues to qualify for the trial and at all visits after the Baseline Visit.
- j. Full physical and neurological examinations should be completed at the Screening Visit and at Week 27. The physical examination should include height at the Screening Visit only. Physical and/or neurological examinations can be done at any time point during the trial at the investigator’s discretion.
- k. Duplicate measurements of blood pressure and heart rate will be obtained supine (after 5 minutes of rest) and 1 measurement of blood pressure and heart rate will be obtained on standing (2 minutes after rising from supine to standing).
- l. The postdose ECG will be obtained at ~1 hour after administration of the first dose of IMP at the Baseline Visit just prior to the time of collection of the PK blood sample. ECGs at all postbaseline visits will be obtained just prior to the time of collection of the PK blood sample.
- m. A triplicate set of ECGs is 3 consecutive ECGs collected 1 to 2 minutes apart over a 5-minute period.
- n. All adverse events that are observed by trial personnel or volunteered by the subject in response to open-ended questioning will be recorded from the first dose of IMP through the end of the Safety Follow-up Period. Serious adverse events will be followed until resolution.

- o. Individual sites may require subjects to have COVID-19 testing done prior to randomization. COVID-19 testing may be performed after randomization per the principal investigator's discretion.
- p. Dipstick urinalysis results are not to be recorded on the eCRFs; any clinically significant abnormality should be captured as an adverse event.
- q. For women of childbearing potential only. All positive urine dipstick pregnancy tests must be confirmed by a serum test. Pregnancy tests can be performed at any time during the trial at the discretion of the investigator. Female subjects with exclusively the same sex partners may not be required to have pregnancy tests per investigator discretion; confirmation with the medical monitor is required.
- r. A urine drug screen is required at screening (see exclusion criteria for exclusions based on the urine drug screen) and may be obtained at other times, at investigator discretion, if use of prohibited drugs is suspected.
- s. PK samples will be collected ~1 hour after administration of the first dose (Day 1) and at the clinic visits at the end of Weeks 5, 11, 14, 22, and 27 just after ECG acquisition at each time point. The date and time of the most recent dose, the dose amount, and the time of the blood draw will be recorded.
- t. Future biospecimen research sample is optional and is to only be collected if signed consent is obtained from the subject.
- u. The first dose of IMP (at the Baseline Visit) will be taken in the clinic; all other doses will be taken on an outpatient basis. Subjects will be instructed to bring their IMP to each clinic visit. Compliance will be assessed through self-reporting by the subject and by tablet count.
- v. Prolactin results will be blinded.
- w. At Week 11 or later (for participants who have passed this visit), participants will be instructed to schedule at their first opportunity a complete eye examination, including evaluation of IOP, to evaluate for glaucoma or glaucoma risk factors at their first opportunity. For additional information on eye examination please refer to Protocol Version 4.0. If the eye examination results are normal, no further examinations are required. If the eye examination results show ocular findings consistent with glaucoma or an increased risk of glaucoma, ophthalmologic follow-up is recommended in 6 months or within 4 weeks of EOT, whichever is sooner. Any more frequent ophthalmologic follow-up may be recommended at the discretion of the ophthalmologist, optometrist, or PI. If the eye examination results are abnormal but not consistent with glaucoma or its risk factors, ophthalmologic follow-up may be done at the discretion of the ophthalmologist, optometrist, or PI and additional eye examinations are no longer required per protocol for safety monitoring.
- x. Ophthalmologic follow-up (6 months after prior examination or within 4 weeks of EOT, whichever is sooner) is only for participants whose first examination showed ocular findings consistent with glaucoma or an increased risk of glaucoma. If additional ophthalmologic follow-up due to ocular findings consistent with glaucoma or an increased risk of glaucoma is suggested by the ophthalmologist or optometrist, contact the medical monitor with results of the eye examination for further discussion.

9.3. EQ-5D-5L Dimensions

EQ-5D-5L Dimensions (UK English Sample Version)

Dimensions	Item	Coded Value
Mobility	I have no problems in walking about	1
	I have slight problems in walking about	2
	I have moderate problems in walking about	3
	I have severe problems in walking about	4
	I am unable to walk about	5
Self-care	I have no problems washing or dressing myself	1
	I have slight problems washing or dressing myself	2
	I have moderate problems washing or dressing myself	3
	I have severe problems washing or dressing myself	4
	I am unable to wash or dress myself	5
Usual activities (e.g., work, study, housework, family or leisure activities)	I have no problems doing my usual activities	1
	I have slight problems doing my usual activities	2
	I have moderate problems doing my usual activities	3
	I have severe problems doing my usual activities	4
	I am unable to do my usual activities	5
Pain/discomfort	I have no pain or discomfort	1
	I have slight pain or discomfort	2
	I have moderate pain or discomfort	3
	I have severe pain or discomfort	4
	I have extreme pain or discomfort	5
Anxiety/depression	I am not anxious or depressed	1
	I am slightly anxious or depressed	2
	I am moderately anxious or depressed	3
	I am severely anxious or depressed	4
	I am extremely anxious or depressed	5

9.4. Columbia-Suicide Severity Rating Scale (C-SSRS) Suicidal Ideation and Suicidal Behavior Scores

The C-SSRS is comprised of 10 categories with binary responses. The 10 categories include:

Category 1 – Wish to be Dead

Category 2 – Non-specific Active Suicidal Thoughts

Category 3 – Active Suicidal Ideation with Any Methods (Not Plan) without Intent to Act

Category 4 – Active Suicidal Ideation with Some Intent to Act, without Specific Plan

Category 5 – Active Suicidal Ideation with Specific Plan and Intent

Category 6 – Preparatory Acts or Behavior

Category 7 – Aborted Attempt

Category 8 – Interrupted Attempt

Category 9 – Actual Attempt (non-fatal)

Category 10 – Completed Suicide

Categories 1-5 represent Suicidal Ideation and categories 6-10 represent Suicidal Behavior. Each category is scored as 1 if there is a positive response in the category and a 0 if there are no positive responses in the category.

- Self-Injurious Behavior Without Suicidal Intent During Treatment

A subject will be categorized as having self-injurious behavior without suicidal intent if there is an occurrence of non-suicidal self-injurious behavior on the C-SSRS – Since Last Visit eCRF at any post-baseline visit.

- Baseline C-SSRS Score

Baseline represents the pre-treatment assessment of recent history, with elements of suicidal ideation assessed over the prior 6 months and elements of suicidal behavior assessed over the prior 2 years. It is scaled from 0 (no suicidal ideation or behavior) to 10 (completed suicide)

- Treatment-Emergent Suicide-Related Event

A subject will be categorized as having a treatment-emergent suicide-related event if at least one post-baseline suicidal ideation or suicidal behavior score is greater than 0.

- Treatment-Emergent Suicidal Ideation Compared to Recent History

A subject will be categorized as having treatment-emergent suicidal ideation compared to recent history when there is at least one post-baseline suicidal ideation score > 0 and is an increase from baseline. Lifetime scores are not considered for baseline suicidal ideation responses.

- Treatment-Emergent Serious Suicidal Ideation Compared to Recent History

A subject will be categorized as having treatment-emergent serious suicidal ideation compared to recent history if the baseline score was < 4 and the post-baseline suicidal ideation score increases to 4 or 5. Lifetime scores are not considered for baseline suicidal ideation responses.

- Emergence of Serious Suicidal Ideation Compared to Recent History

A subject will be categorized as having emergence of serious suicidal ideation compared to recent history if baseline score was 0 (no suicidal ideation) and post-baseline C-SSRS suicidal ideation score is either 4 or 5. Lifetime scores are not considered for baseline suicidal ideation responses.

- Emergence of Suicidal Behavior Compared to all Prior History

A subject will be categorized as having emergence of suicidal behavior compared to all prior history if there had been no suicidal behavior in Categories 6-10 reported at any pre-treatment assessment, including responses to lifetime history questions, and there is at least one positive post-baseline C-SSRS assessment in Categories 6-10. 'All Prior History' represents lifetime history.

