8.	
Subjects who answer “yes” on the C-SSRS Suicidal Ideation Item 4 or Item 5 (Active Suicidal Ideation with Some Intent to Act, Without Specific Plan, or Active Suicidal Ideation with Specific Plan and Intent) and whose most recent episode meeting the criteria for C-SSRS Item 4 or Item 5 occurred within the last 6 months, OR
 
Subjects who answer “yes” on any of the 5 C-SSRS Suicidal Behavior Items (actual attempt, interrupted attempt, aborted attempt, preparatory acts, or behavior) and whose most recent episode meeting the criteria for any of these 5 C-SSRS Suicidal Behavior Items occurred within the last 2 years, OR
 
Subjects who, in the opinion of the investigator, present a serious risk of suicide.

9.	Subjects with substance abuse or dependence disorder, including alcohol, benzodiazepines, and opioids, but excluding nicotine, within the past 6 months (180 days).
10.	Subjects with dementia or cognitive impairment that, in the judgement of the investigator, would exclude the subject from understanding the ICF or participating in the trial.
11.	Subjects with any condition that could possibly affect drug absorption, including bowel resections, bariatric weight loss surgery, or gastrectomy (this does not include gastric banding).
12.	
Subjects who have a positive result for HIV antibodies, HbsAg, or HCV antibodies at screening.
 
Note: Subjects who were previously infected with hepatitis C but have been successfully treated (defined as a sustained virologic response or undetectable hepatitis C viral RNA levels at 12 or more weeks after the end of treatment) may be enrolled after discussion with the medical monitor.

13.	Subjects with a history of malignancy other than: 
 Non-metastatic basal or squamous cell carcinoma of the skin or carcinoma in situ that was surgically removed in total >1 year before signing the ICF and had not recurred Another type of malignancy that had been in remission for ≥ 5 years before signing the ICF and had not recurred

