8.3.3 Columbia-Suicide Severity Rating Scale

Suicidality will be monitored during the trial using the C-SSRS. This semi-structured interview was originally developed to evaluate the link between antidepressants and suicidal behavior and ideation in youth and AEs from pediatric clinical trials ([Posner et al, 2011](#)). It was designed to quantify the severity of suicidal ideation and behavior. Trial personnel who administer the C-SSRS must complete the appropriate training and have valid certification. Training on the scale will be provided via the sponsor.

This trial will use the “Baseline/Screening” and “Since Last Visit” versions of the scale. The “Baseline/Screening” version, which assesses the lifetime experience of the subject with suicide events and suicidal ideation and the occurrence of suicide events or ideation within a specified time period prior to entry into the trial, will be completed for all subjects at screening to determine eligibility and confirmed at baseline. Any subject with active suicidal ideation or suicidal behaviors within the last 6 months, suicidal behaviors within the last 2 years, or who in the clinical judgment of the investigator presents a serious risk of suicide should be excluded from the trial ([Section 5.2, exclusion 8](#)).

The “Since Last Visit” C-SSRS form will be completed at all visits after screening and baseline. The investigator will review the results of the “Since Last Visit” C-SSRS during the trial to determine whether it is safe for the subject to continue in the trial. If a subject demonstrates potential suicidal ideation associated with actual intent or method or plan as indicated by “YES” answers on item 4 or 5 of the C-SSRS, the investigator will evaluate whether a risk assessment by a qualified mental health professional (or the investigator alone if the investigator is a qualified mental health professional) is needed and whether the subject should continue in or be discontinued from the trial.

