5.15.9. Columbia-Suicide Severity Rating Scale (C-SSRS)

The maximum post-baseline results from the C-SSRS will be summarized. The maximum of each subscale (suicidal ideation [Categories 1-5], suicidal behavior [Categories 6-10], suicidal ideation or behavior [Categories 1-10], and self-injurious behavior without suicidal intent) will be presented. The number of patients with suicide-related treatment-emergent events, treatment-emergent suicidal ideation, and suicidal behavior, based on a comparison of the C-SSRS at baseline and/or previous lifetime experience to maximum C-SSRS scores across all post-baseline assessments will be provided. All C-SSRS elements will be reflected in a listing.

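### SAP 9.4 counts any post-baseline C-SSRS score above 0 as a treatment-emergent suicide-related event, although SAP 5.15.9 bases that count on a comparison with baseline or lifetime history (minor)

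*SAP*

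**What the plan says.** SAP 3.2.5 refers the reader to SAP 9.4 for the definitions of treatment-emergent C-SSRS events. There, the composite event is met "if at least one post-baseline suicidal ideation or suicidal behavior score is greater than 0". Neither baseline nor lifetime history enters the definition.

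SAP 5.15.9 describes the table. It covers "The number of patients with suicide-related treatment-emergent events, treatment-emergent suicidal ideation, and suicidal behavior", and states that these are "based on a comparison of the C-SSRS at baseline and/or previous lifetime experience to maximum C-SSRS scores across all post-baseline assessments".

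The other four emergence definitions in SAP 9.4 all carry a pre-treatment condition. Treatment-emergent ideation needs "at least one post-baseline suicidal ideation score > 0 and is an increase from baseline". The two serious-ideation categories need a baseline below 4 and a baseline of 0 respectively. Emergence of behavior applies only "if there had been no suicidal behavior in Categories 6-10 reported at any pre-treatment assessment, including responses to lifetime history questions". The baseline itself is defined, with "elements of suicidal ideation assessed over the prior 6 months and elements of suicidal behavior assessed over the prior 2 years".

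**The concern.** A programmer who follows 9.4 departs from 5.15.9, and one who follows 5.15.9 finds no definition for the composite it promises.

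The direction of the error is clear. A subject with category 2 ideation before treatment and a post-baseline maximum of category 2, or of category 1, is tabulated as having an event that emerged on treatment. By the comparison in 5.15.9 nothing emerged.

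C-SSRS is a listed safety endpoint. The composite row would mix persisting or improving pre-treatment ideation with new events, and would not reconcile with the ideation and behavior rows beside it, which do use pre-treatment status. It also adds no information: 5.15.9 already presents the post-baseline maximum over categories 1 to 10, and a maximum above 0 there picks out the same subjects.

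**Working it through.** The documents give no figure on this point, so there is none to reproduce. The check compares the rules over every ideation score pair that eligibility allows.

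**Inputs**

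- Rule A (SAP 9.4 composite, ideation part): post-baseline maximum > 0.
- Rule B (baseline comparison, as in the 9.4 ideation definition): post-baseline maximum > 0 and > baseline.
- Post-baseline maximum ideation score: 0 to 5, six values.
- Baseline ideation score: depends on which eligibility text applies.
  - Exclusion 8 in protocol 5.2 removes subjects who report Item 4 or 5 ideation and "whose most recent episode meeting the criteria for C-SSRS Item 4 or Item 5 occurred within the last 6 months". It also removes those with suicidal behavior in the last 2 years or a serious suicide risk in the investigator's opinion. Categories 1 to 3 are not barred by item, so baseline can be 0 to 3.
  - Protocol 8.3.3, repeated in SAP 3.2.5, is broader: "Any subject with active suicidal ideation or suicidal behaviors within the last 6 months" should be excluded. SAP 9.4 names categories 2 and 3 as active thoughts or ideation, but category 1 is a wish to be dead. Read strictly, baseline can be 0 or 1.

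**Baseline 0 to 3**

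- All pairs: 4 × 6 = 24.
- Rule A flags 4 × 5 = 20.
- Rule B flags 5 + 4 + 3 + 2 = 14.
- Flagged by A only: 20 − 14 = 6. As (baseline, maximum), three are unchanged, (1,1), (2,2), (3,3), and three are improved, (2,1), (3,1), (3,2).

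**Baseline 0 to 1**

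- All pairs: 2 × 6 = 12.
- Rule A flags 2 × 5 = 10.
- Rule B flags 5 + 4 = 9.
- Flagged by A only: 10 − 9 = 1, the pair (1,1).

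These are score combinations. They are not equally likely and are not patients.

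**Behavior part.** A behavior recorded on the form covering the time since the last visit is a new act in that interval, so a score above 0 without a baseline term causes no comparable problem. The overcount comes from ideation.

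**Effect between arms (assumed rates only).** Suppose a fraction p of each arm has persisting ideation and, separately, 2% on tavapadon and 1% on placebo have true emergence.

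- p = 4%: the table shows 6% against 5%, ratio 1.2, difference 1 point.
- p = 1%: the table shows 3% against 2%, ratio 1.5, difference 1 point.
- p = 0: 2% against 1%, ratio 2.0, difference 1 point.

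The ratio moves toward 1 and the difference does not change.

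**The case against.** **The composite may be a deliberate any-occurrence category.** The other four definitions name their comparison in the title and this one does not. That is plausible as intent, but 5.15.9 lists this event first and attaches the comparison after the whole list. If any-occurrence was meant, the label and 5.15.9 need changing.

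**The SAP's adverse-event convention needs no worsening.** SAP 3.2.3.2 treats an event on or after the first dose as treatment-emergent. But for a pre-existing condition, the protocol's list of adverse events (10.3.1) looks to exacerbation. The analogy does not remove the conflict between 9.4 and 5.15.9.

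**Nothing is carried forward from history.** Post-baseline forms ask about the interval since the last visit, so each positive score is an on-study report. This is true, and for behavior it is decisive. For ideation, a state that merely continues is still reported and counted as emergent.

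**Little is hidden.** Baseline-compared ideation and behavior rows, the categories 1 to 10 maximum and a full listing are all planned. This stands, and it is the main reason the point is minor.

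**Stronger readings the documents do not support.** A reader might infer that all the C-SSRS emergence counts ignore baseline; only this composite does. A reader might infer that the rule favors one arm or masks a signal of known size. The rule is identical in both arms, no hypothesis test is attached, the rates above are assumptions, and the risk difference in them is unchanged. Nor does any document rank this row above the others.

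**Conclusion.** Wrong as written, and minor. SAP 9.4 and 5.15.9 contradict each other on one composite safety count, and following 9.4 labels unchanged or improved pre-treatment ideation as treatment-emergent.

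The extent is between 1 of 10 and 6 of 20 flagged ideation score pairs, depending on whether the stricter eligibility wording or exclusion 8 governs. Those two texts differ although protocol 8.3.3 cites exclusion 8, and should be reconciled. The documents do not say how many subjects have baseline ideation, so the overcount in patients is unknown. The conclusion rests on reading the comparison clause in 5.15.9 as covering all three items before it, which is the plain reading.

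**What to change.** In SAP 9.4:

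1. Retitle the present count *any post-baseline suicidal ideation or behavior*, with its rule unchanged.
2. Define the treatment-emergent suicide-related event as either a post-baseline ideation score above 0 that is an increase from the recent-history baseline, or any post-baseline suicidal behavior (categories 6 to 10) on the Since Last Visit form, whatever the lifetime history.

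The behavior part should not borrow the no-prior-history condition from the separate behavior definition. Exclusion 8 does not by item bar subjects whose last suicidal behavior was more than 2 years ago. With that condition, a new attempt on treatment in such a subject, without a rise in ideation, would drop out of the composite.

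Then align 5.15.9: the comparison clause applies to the ideation part of the new composite, and the retitled row is exempt from it. The cost is one definition, one retitled row and one extra table row, with no new data. The least that would resolve the contradiction is to retitle the row and exempt it in 5.15.9, but that leaves no baseline-compared composite.
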